## Study Treatment and Duration

Product name:	Belantamab mafodotin	Pembrolizumab
[Formulation description:]	20 mg/mL, 1.5 mL/vial	100 mg/4 mL
Route of Administration	Delivered as IV infusion. Refer to Study Reference Manual (SRM) for details.	Delivered as 30 min IV infusion

### Treatment Duration

Belantamab mafodotin and pembrolizumab will be administered via intravenous (IV) infusion on day 1 of each 21-day cycle (once every 3 week dosing schedule). Subjects enrolled in Part 1 and 2 will be treated until disease progression, intolerable toxicity, informed consent withdrawal, or for a maximum of 35 cycles (approximately 2 years, See Combination Treatment Schematic below).

## Combination Treatment Schematic

### **Dosing:**

- Belantamab mafodotin and pembrolizumab on D1 of each cycle
- Belantamab mafodotin first, Pembrolizumab as second iv infusion (1hr apart)
- If IRR related to GSK2857916, the PD1 dosing will be delayed
- Max treatment duration: 35 cycles combination treatment

[figure not shown]
Subjects who discontinued treatment for reasons other than PD will be followed up every 3 weeks until confirmed PD, initiation of a new anticancer therapy or death. All subjects with confirmed PD will be followed for OS every 3 months until the end of study. End of study is defined as when all subjects have been followed for 36 months from first dose of study treatment, or died, or withdrew consent, or are lost to follow-up, or the study is early terminated, whichever occurs first. The next subsequent therapy will be collected for all subjects who have confirmed PD before initiation of new anticancer therapy.

### **Treatment Arms**

The study will comprise of two parts: Part 1- dose escalation and Part 2- expansion.

#### **Part 1: Dose Escalation**

Part 1 dose escalation will characterize the safety and tolerability of escalating doses of belantamab mafodotin in combination with 200 mg pembrolizumab to establish the RP2D. The following dose levels of belantamab mafodotin in combination with 200 mg pembrolizumab are planned to be studied: 2.5 mg/kg (dose level [DL] 1) and 3.4 mg/kg (DL2) (as outlined in Dose Escalation Schematic for Part 1 below). Additionally, other dose levels may also be explored. Dose level 1.92 mg/kg may be tested if dose level 2.5 mg/kg is not cleared. During the dose escalation, at least 3 evaluable subjects will be studied per dose level. In Part 1, any subject who received at least one treatment cycle of the combination will be evaluated for DLTs. Subjects who have received only belantamab mafodotin or have been withdrawn from the study for reasons other than toxicity but prior to completion of DLT observation period will be replaced.

[figure not shown]
**Dose Escalation Schematic for Part 1****Dose Limiting Toxicity Criteria (Part 1 only)**

The DLT observation window will be 21 days (=1 cycle). Any subject in Part 1 who received at least one treatment cycle of the combination of belantamab mafodotin and pembrolizumab will be evaluated for DLTs using National Cancer Institute (NCI) CTCAE Version 4.03 [NCI, 2010]. In addition, for belantamab mafodotin treatment related corneal events, the GSK grading scale for corneal events ([Appendix 9](#)) should be used for evaluation of DLT.

A DLT is defined as an AE that meets at least one of the criteria defined below and is considered by the investigator to be clinically relevant and attributed (definitely, probably, or possibly) to the study therapy during the 21 day DLT observation period.

1. Any Grade 4 non-hematologic toxicity
2. Any Grade 3 non-hematologic toxicity, with the following exceptions (i.e., the following will not be considered a DLT): Grade 3 diarrhea, nausea, or vomiting that responds to standard of care within 72 hours; Grade 3 hypertension (controlled following addition of 1 antihypertensive medication); and Grade 3 tumor lysis syndrome
3. Any Grade 3 or greater non-hematologic laboratory value if either:
  - The laboratory abnormality persists for >48 hrs despite supportive treatment, or
  - The abnormality leads to hospitalization
4. Hematologic toxicity:
  - Grade 4 hematologic toxicity lasting  $\geq 7$  days, except thrombocytopenia:
    - Grade 4 thrombocytopenia of any duration
    - Grade 3 thrombocytopenia associated with clinically significant bleeding
  - Grade 3 or greater febrile neutropenia lasting >48 hours despite adequate treatment:

CCI

5. Nephrotoxicity requiring dialysis, and not considered to be due to disease under study (ie. myeloma) based on investigator's assessment
6. Liver toxicity meeting pre-specified GSK liver stopping criteria
7. Prolonged delay (>14 days) in initiating Cycle 2 due to any treatment (pembrolizumab or belantamab mafodotin) related toxicity, with the exception of Grade 1-2 corneal events (GSK grading scale for belantamab mafodotin treatment related corneal events)
8. Any treatment-related toxicity that causes the subject to discontinue treatment during Cycle 1
9. Any other toxicity considered to be dose-limiting that occurs beyond 21 days will be considered in the selection of the dose to recommend for expansion cohorts
10. Any other event which in the judgment of the investigator and GSK Medical Monitor is considered to be a DLT

A subject who develops a DLT will be allowed to continue on study treatment if the toxicity did not meet predefined stopping criteria and recovered to  $\leq$  Grade 1 within 14 days if the investigator and medical monitor agree that for a given subject the potential benefits may outweigh the risks.

The dose escalation will complete when RP2D is determined. The RP2D will be the maximum pre-specified dose of 3.4 mg/kg, or a lower dose that provides adequate PK exposure, tolerability and clinical activity.

### **Recommended Phase 2 Dose (RP2D)**

All available data from Part 1 will be analyzed after the last cohort of subjects complete the 21-day DLT observation period. Data considered for RP2D selection will include, but not be limited to: safety, available PK profile, and observed signs of clinical activity. A dose level below maximum pre-specified dose (3.4 mg/kg) may be selected as RP2D if compelling safety and encouraging clinical activity can be demonstrated at dose levels below 3.4 mg/kg.

### **Part 2: Expansion**

Once the RP2D has been identified, an expansion cohort (Part 2) will open for enrollment of up to 28 subjects with RRMM in order to confirm the safety profile and to evaluate the clinical activity of the combination.

If necessary, alternative schedules and/or additional dose(s) can be explored after RP2D is identified.

## Safety Assessment

Safety assessments during the study will include, but not limited:

- AEs, SAEs, AEs leading to discontinuation of study treatment
- Clinical laboratory safety assessments, including hematology and clinical chemistry data
- Other safety measures, including data for vital signs, the performance status of the ECOG scale, ECG, echocardiogram (ECHO), and serum pregnancy test for female subjects of childbearing potential
- Ocular exam

### Corneal Supportive Care Guidelines (belantamab mafodotin)

Corneal events, which commonly manifest as a superficial microcystic keratopathy, have previously been observed with antibody drug conjugates, including those conjugated to MMAF. It is required that sites establish a close collaboration with an ophthalmologist (or optometrist, if ophthalmologist is not available) who will be responsible for assessing subjects on study and managing subjects who develop a corneal event in close communication with the GSK Medical Monitor and possibly a GSK ophthalmologist.

Subjects will be assessed by ophthalmologists (or optometrist, if ophthalmologist is not available) at baseline, and then every three weeks prior to each dose of belantamab mafodotin for the first 4 doses. After the 4th dose of belantamab mafodotin, if there are no significant ocular symptoms or vision changes, the frequency of ophthalmologic exams may be decreased to once every 6 months until end of study treatment. In case of persistent or newly developed ocular symptoms or vision changes, the subject will have further ophthalmologic exams, at least every 3 months until resolution (to Grade 1 or baseline) or more frequently as clinically indicated by the eye care specialist.

Further information regarding corneal event associated with belantamab mafodotin, including a grading scale and prophylactic measures are in [Appendix 9](#).

## Clinical Activity Assessment

Standard disease assessments for MM will include laboratory tests (serum and urine M protein test, sFLC, and corrected calcium), bone marrow core biopsy and aspirate (in case of suspected CR or to demonstrate progression), immunohistochemistry (IHC) of bone marrow samples to confirm sCR to confirm stringent CR) or imaging, and minimal residual disease by Next Generation Sequencing (NGS; in subjects with achieve confirmed VGPR or CR). Response evaluation will be performed according to the International Myeloma Working Group Uniform Response Criteria for Multiple Myeloma 2016 [[Kumar](#), 2016]. Minimal residual disease negative rate will be assessed in those subjects who achieve a VGPR or CR.

## Pharmacokinetic assessments

Blood PK samples will be collected during the trial and analysed for belantamab mafodotin (ADC and total antibody) and cys-mcMMAF concentrations. Blood samples for pembrolizumab measurements will be collected and stored, but will only be analyzed in case of unexpected clinical findings.

## Translational Research

BCMA expression in plasma cells from bone marrow aspirates will be evaluated at baseline, and at additional timepoints if available, by IHC. IHC markers may include but will not be limited to: BCMA, Blimp1, CD138, and CD38.

Soluble BCMA (sBCMA) concentrations in serum will be evaluated in all subjects.

Additionally, bone marrow tumor tissue may be evaluated for any DNA/RNA changes correlating with clinical response.

## Value Evidence and Outcome

The impact of potential ocular toxicity will be assessed using the selected items from the Questionnaire of NEI-VFQ-25 and OSDI.

A subset of items selected from the PRO-CTCAE Version 1.0 Item library will be applied to evaluate symptomatic toxicity in subjects.

Subjects enrolled in Part 2 only will self-complete additional questionnaires to assess the symptoms related to multiple myeloma and its treatment, and the impact of these symptoms on daily functioning. Symptoms will be assessed using two questionnaires: EORTC-QLQ-C30 and EORTC-QLQ-MY20.

To further evaluate disease and treatment related symptoms and associated impacts on function and health-related quality of life, subjects enrolled in both Part 1 and 2 will participate in an Exit Interview conducted via telephone subsequent to the End of Treatment visit.

## Statistical Analysis

For part 1, no formal statistical hypotheses are being tested. In Part 1, the dose escalation decisions will be guided by the Modified Toxicity Probability Interval (mTPI) approach, as well as the totality of the safety data. After the last cohort of subjects in Part 1 completes the 21-day DLT observation period, a formal interim analysis will be performed to support the RP2D decision, except for scenarios where RP2D is clearly defined by the toxicity profile.

The primary goal of Part 2 is to confirm safety and to characterize clinical activity of the combination and to detect if meaningful overall response rate (ORR) can be achieved.

During part 2 of the study, treatment-rated Grade 4 or higher AEs will be continuously monitored starting from when 5 subjects are dosed. If observed toxicity level is significantly higher than 12% at 1-sided alpha of 0.025, the study may be terminated early based on totality of safety data. The 12% threshold is chosen based on 11% Grade 4 or higher AE observed in study BMA117159.

For Part 2, futility analyses for ORR will start when 10 subjects are evaluable. Enrollment may stop if the stopping rule is met based on totality of data.

Primary analysis of the data captured in Part 1 and Part 2 will be performed approximately 15 months from the last subject first visit (LSFV) to test the hypothesis that a meaningful response rate (ORR) can be achieved of the combination. Participants may discontinue the study treatment if meaningful response rate (ORR) cannot be achieved. For primary analysis, data may be combined from parts 1 and 2.

Final analysis of the data captured in Part 1 and Part 2 will be undertaken after all subjects meet at least one of the following criteria: have reached the end of study or died. End of study is defined as when all subjects have been followed for 36 months from first dose of study treatment or died or withdrew consent or are lost to follow-up or the safety stopping criteria is met, whichever occurs first.

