### **9.1.2. Part 2: Expansion cohort**

The primary goal of Part 2 is to characterize clinical activity of the combination and to detect if meaningful response rate (ORR) can be achieved. Based on historical information [[Lokhorst](#), 2015] and clinical judgement, the null hypothesis has been defined as  $ORR \leq 40\%$ . The alternative hypothesis has been defined as  $ORR \geq 60\%$  based on clinically meaningful improvement of 20%.

In Part 2, treatment-related Grade 4 or higher AEs will be continuously monitored starting from when 5 subjects are dosed. Based on the 11% Grade 4 or higher AEs observed in the FTIH study (BMA117159), it is considered that the combination treatment has unacceptable toxicity if observed treatment-related Grade 4 or higher AEs is significantly higher than 12% at 1-sided alpha of 0.025.

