### **9.2.2. Part 2: Expansion Cohort**

Sample size for Part 2 is estimated based on hypothesis specified in Section [9.1.2](#) using the Predictive Probability design [[Lee](#), 2008]. Details of sample size calculation are provided in [Appendix 12](#). The optimal design has  $N_{max} = 28$ , type I error rate of 0.10 and power of 80.6%. The expansion cohort may be stopped early for futility if the predicted probability of success is less than 1.5%. If the true ORR is 40%, the expected sample size is 20 and the probability of early termination is 86.1%; if the true ORR is 60%, the expected sample size is 28 and the probability of early termination is 15.6%.

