**Table 13 Safety Stopping Rules for the Expansion Cohort**

Number of dosed subjects	Stop if treatment related Grade 4 or higher AEs larger or equal to this number
5	3
6-10	4
11-14	5
15-19	6
20-25	7
26-28	8

Interim analyses for ORR will start when at least 10 subjects are evaluable as defined in Section [9.4.1](#). Subjects who initially received RP2D in Part 1 may also be included. The observed number of subjects with unconfirmed response of PR or better will be compared with the stopping boundary in [Table 14](#). Enrolment may stop if the stopping rule is met. Final decision will be based on the totality of data. For example, if there are 2 unconfirmed responses out of 10 evaluable subjects, enrolment may stop after review of all available data; if there are 3 or more unconfirmed responses out of 10 evaluable subjects, enrolment will continue.

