## 9.6. Primary Analysis

Primary analysis will be conducted approximately 15 months from the last subject first visit (LSFV). If meaningful response rate (ORR) cannot be achieved, participants may discontinue the study treatment and will undergo end of treatment and follow-up assessments as defined in Section 4.2.2. Statistical considerations and data analysis may be performed separately and/or combined for Part 1 and Part 2.

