**Table 15 Statistical Analysis Methods for Clinical Activity Endpoints (Part 2)**

Endpoint	Statistical Analysis Methods
Primary	
Overall Response Rate (ORR) is defined as the percentage of subjects with a confirmed PR or better (i.e. PR, VGPR, CR and sCR), according to the International Myeloma Working Group (IMWG) Response Criteria.
 
The number and percentage of subjects in the following response categories will be presented: sCR, CR, VGPR, PR, overall response (sCR+CR+VGPR+PR), minimal response (MR), stable disease (SD), progressive disease (PD), and not evaluable (NE). The corresponding 95% CI for ORR will also be provided. Subjects with unknown or missing responses will be treated as non-responders, i.e., these subjects will be included in the denominator when calculating percentages of response.

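### Part 1 data may optionally enter the primary ORR test, but the hypothesis, the 0.10 / 80.6% and the only success cut-off belong to a 28-patient Part 2

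*Protocol*

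**What the plan says.** The synopsis (Statistical Analysis) says that the primary analysis, about 15 months after the last subject's first visit, covers data from both parts and is done "to test the hypothesis that a meaningful response rate (ORR) can be achieved of the combination". It then allows pooling: "For primary analysis, data may be combined from parts 1 and 2". Section 9.6 says: "Statistical considerations and data analysis may be performed separately and/or combined for Part 1 and Part 2".

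The design figures sit elsewhere and are tied to Part 2:

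- Section 9.1.2 sets the null (ORR at most 40%) and the alternative (at least 60%) under the Part 2 heading.
- Section 9.2.2 gives, for a maximum of 28, a "type I error rate of 0.10 and power of 80.6" per cent.
- Table 14 ends at 28 evaluable subjects, where 14 or fewer responses fail. Success is therefore 15 or more of 28, by implication; no other cut-off appears.
- Section 9.1.1 says that Part 1 carries no formal hypothesis and will be analysed by descriptive methods only.
- Table 15, which holds the ORR analysis, is headed as a Part 2 table.

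Two further passages bear on the point. For the ORR interim looks, Section 9.5.2 says: "Subjects who initially received RP2D in Part 1 may also be included". On the choice of dose, the synopsis says: "Data considered for RP2D selection will include, but not be limited to: safety, available PK profile, and observed signs of clinical activity". Section 4.2.3.2 says the same in substance.

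**The concern.** A test has a type I error only once its data set and its cut-off are both fixed. Here the data set is optional and the cut-off exists for one of the options only. A reader of Section 9.2.2 would take 0.10 and 80.6% as properties of the primary analysis, but they hold only if the option to pool is not used.

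Three separate faults follow. The choice between Part 2 alone and pooled data is open in an open-label trial. No cut-off is given for more than 28 patients, and nothing says whether pooling would cover RP2D patients only or all Part 1 doses. And Part 1 responses that helped to choose the dose could be counted again in the test of that dose.

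At stake is the error rate attached to the trial's one formal efficacy claim, and an ORR that may lean upward if Part 1 responders influenced the dose.

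**Working it through.** **Inputs from the protocol.** p0 = 0.40 and p1 = 0.60 (Section 9.1.2); maximum 28, type I error 0.10, power 80.6% (Section 9.2.2); futility boundary b(n) for n = 10 to 27 and failure at 14 or fewer of 28 (Table 14); up to 6 subjects per Part 1 dose level (Section 9.2.1). One dose level added to Part 2 therefore gives 28 + 6 = 34.

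**Assumptions, because the protocol gives no pooling rule.** Six RP2D patients are added. The pooled cut-off is the smallest r with exact one-sided level at most 0.10: P(X ≥ 17 | 34, 0.4) = 0.155 and P(X ≥ 18 | 34, 0.4) = 0.087, so r = 18. Both futility settings are shown, because Section 9.5.2 lets the boundary be overruled on the totality of data.

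**Step 1. The stated design reproduces.** Let f(n, s) be the probability of having s responses after n patients without having stopped:

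f(n, s) = f(n−1, s)(1−p) + f(n−1, s−1)p, set to 0 when s ≤ b(n).

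Success is the sum of f(28, s) over s ≥ 15.

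- p = 0.4: 0.0997. Probability of reaching 28 is 0.1390, so early termination is 86.1%, as stated.
- p = 0.6: 0.8055, against the stated 80.6%.
- Boundary never followed: 0.1025 and 0.813.

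Part 2 alone at 15 of 28 thus delivers the stated figures.

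**Step 2. A pooled test fixed in advance at 18 of 34, unselected patients.** Type I error is 0.072 with the boundary followed and 0.087 without it. Both are below 0.10.

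**Step 3. Taking whichever of Part 2 alone or pooled succeeds.** Let X be the Part 2 responses and Y the responses among 6 Part 1 patients, Y ~ Bin(6, 0.4). Then P(Y ≥ 4) = 0.1792, P(Y ≥ 5) = 0.0410 and P(Y = 6) = 0.0041.

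- *Boundary followed.* Anyone reaching 28 had at least 14 responses at n = 27, so the only extra route to success is X = 14 with Y ≥ 4. f(28, 14) = 0.1390 − 0.0997 = 0.0393. Result: 0.0997 + 0.0393 × 0.1792 = 0.1068, or 10.7%.
- *Boundary always ignored.* P(X = 14) = 0.0844, P(X = 13) = 0.1181, P(X = 12) = 0.1440. Result: 0.1025 + 0.0844 × 0.1792 + 0.1181 × 0.0410 + 0.1440 × 0.0041 = 0.1230, or 12.3%.

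**Step 4. The same, with worst-case dose selection.** Two doses with equal true ORR, 6 patients each, and the better-responding one chosen. Y becomes the larger of two Bin(6, 0.4) counts, so P(Y ≥ 4) = 1 − 0.8208² = 0.3263.

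- *Boundary followed:* 0.0997 + 0.0393 × 0.3263 = 0.1125, or 11.3%.
- *Boundary always ignored:* 0.1406, or 14.1%.

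**Step 5. The only printed cut-off, 15, kept for 34 patients.**

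- *Boundary followed:* P(Y ≥ 1) = 1 − 0.6⁶ = 0.9533, so 0.0997 + 0.0393 × 0.9533 = 0.1372, or 13.7%.
- *Boundary ignored:* P(X ≥ 15 | 34, 0.4) = 0.373, or 37%.

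| Rule (true ORR 40%) | Futility followed | Futility ignored |
|---|---|---|
| Part 2 only, 15/28 | 0.0997 | 0.1025 |
| Pooled, fixed in advance, 18/34, unselected | 0.072 | 0.087 |
| Better of the two, unselected | 0.107 | 0.123 |
| Better of the two, worst-case selection | 0.113 | 0.141 |
| Pooled, cut-off left at 15/34, unselected | 0.137 | 0.373 |

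**The case against.** **The text leans to Part 2 already.** ORR is the primary endpoint of Part 2 only, the hypothesis is headed Part 2, Part 1 is declared descriptive, and the ORR analysis uses the All Evaluable population, which Section 9.4.1 introduces for Part 2 decisions. This stands as a reason to expect a Part 2 test, but it does not cancel the express permission in the synopsis and Section 9.6. It shows that the passages conflict.

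**The Reporting and Analysis Plan may settle it.** Section 9.8 sends full details there, and that document is not shown. A reader might infer that the sponsor will choose the data set after seeing both results; the protocol does not say so. The objection does not remove the mismatch, because the protocol quotes error rates for one analysis and permits another.

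**Pooling need not inflate the error.** This stands in full. Step 2 shows a pooled test within 0.10, so a general statement that type I error is uncontrolled would be wrong.

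**The selection model is extreme.** This also stands. The dose choice rests on safety and PK as well as activity, and escalation is driven by toxicity. The data are reviewed when the last cohort finishes its 21-day window, whereas evaluability for response needs more than 66 days, so some Part 1 responses would be immature. The selection figures are upper bounds for the either-or rule, not expected values.

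**The confidence interval is not a decision rule.** Table 15 says: "The corresponding 95% CI for ORR will also be provided". The 95% interval at 15 of 28 runs from 33.9% to 72.5% and contains 40%, so a reader might infer that real power is well below 80.6%. The documents do not support that: nowhere is exclusion of 40% by this interval made the criterion for success. Reporting a 95% interval beside a design with a 0.10 error rate is ordinary description.

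**Conclusion.** The point holds in a limited form. The protocol permits an optional pooled primary test with no subject rule and no cut-off above 28, contradicts its own statement that Part 1 is descriptive, and quotes 0.10 / 80.6%, which describe Part 2 alone.

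If a pooled cut-off is recalibrated to 18 of 34 and the better result is taken, the excess over 0.10 is small when futility is followed (10.7%, or 11.3% with worst-case selection). It is larger when every boundary crossing is overruled (12.3% and 14.1%). The excess becomes material if 15 is carried over to 34 patients: 13.7% with futility followed and 37% without.

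These figures assume six added RP2D patients, a true ORR of 40%, and the cut-offs named above. The defects are the open choice, the missing cut-off and the possible reuse of responses that informed the dose. Severity is moderate: this is the trial's only formal efficacy test, but the likely inflation is modest and the repair is simple.

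**What to change.** State in the synopsis, Section 9.6 and Section 9.8.1 that the primary test uses Part 2 subjects only, n = 28, and rejects ORR ≤ 40% if at least 15 have a confirmed partial response or better. Report ORR for Part 2 plus Part 1 subjects treated at the RP2D, with its interval, as a labelled supplementary estimate.

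An equally valid alternative is to pre-specify pooling restricted to RP2D subjects, with its own cut-off and recomputed operating characteristics. That version should say how responses used in choosing the dose are handled.

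Whichever is chosen, make the futility count in Section 9.5.2 consistent with it. Either remove the optional inclusion of Part 1 subjects, or fix it now and recompute Table 14.

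The cost is wording. Under the first option the sponsor gives up at most six RP2D patients in the formal test but keeps them in the supplementary estimate. The second option also needs one recalculation of the design.
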